After giving informed consent to participate in the clinical trial (*Clinical Trial Written Informed Consent Form*), subjects will be assigned a 7-digit subject number by the IWRS and will be examined during the screening period to assess their eligibility for inclusion in the clinical trial. The Investigator will determine whether or not a subject qualifies for inclusion in the clinical trial based on study inclusion and exclusion criteria (Sections 6.1 and 6.2). Eligible individuals will be randomized by the IWRS to one of the treatment arms according to the assigned 5-digit randomization number. The unblinded pharmacist or designee will be responsible for treatment assignment based upon the randomization number for each eligible individual from the IWRS.

Throughout the course of the clinical trial, clinical visits (or telephone contacts) will be scheduled. Study assessments will include physical assessments, infusion vital signs monitoring, blood analysis, walking activity in daily life evaluation, muscle strength measurements, assessments of HRQoL, pain and fatigue, and recording of AEs and concomitant medication.

Individuals are allowed to attend the study centre at any time during the study. If a subject is prematurely withdrawn from the study, he or she will be asked to attend the study centre as soon as possible thereafter so that end of study assessments can be conducted.

Figure 1. Schematic description of clinical trial design

[figure not shown]
[figure not shown]

[figure not shown]
Figure 2. Schematic description of Stage 1 clinical trial design

Abbreviations: 2MWD: Two-Minute Walk Distance; EoTV: End of Treatment Visit; EV: Enrollment Visit; IV: Infusion Visit; SV: Screening Visit; W: Week.

GRIFOLS

Figure 3. Schematic description of Stage 2 clinical trial design

Abbreviations: 2MWD: Two-Minute Walk Distance; EoTV: End of Treatment Visit; EV: Enrollment Visit; IV: Infusion Visit; SV: Screening Visit; W: Week.

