- 6. Physical performance: 2MWD with assessment of perceived exertion/fatigue by Borg scale immediately before and immediately after 2MWD.
- 7. Rest period (sitting on a chair for at least 30 minutes and until the subject feels fully recovered after completion of the 2MWD).
- 8. Endurance: 6MWD with assessment of perceived exertion/fatigue by Borg scale immediately before and immediately after 6MWD.

- *Procedures 9 through 11 must be performed on the same day (on a different day after procedure 8) in the following order:

 9. Muscle strength: MMT.
- 10. Rest period (sitting on a chair for at least 30 minutes and until the subject feels fully recovered after completion of the MMT).
- 11. Muscle strength: QMT.
- 12. Blood testing:
 - Blood biochemistry and cell counts: CBC, including differential leukocyte count, creatinine, BUN, ALT, AST, ALP, TBL, and GFR.
 - Inflammatory cytokines: IL-1, IL-4, IL-6, IL-10, IL-13, IL-17, IL-23, TNF alpha, and IFN-gamma.
 - Retention blood sample for possible future biomarker testing.

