6.3 Subject withdrawal criteria and procedures

A subject's participation in the study may be terminated early under the following circumstances:

- 1. Subject withdraws the informed consent to participate in the clinical trial.
- 2. Subject does not meet all inclusion criteria.
- 3. Subject meets any of the exclusion criteria.
- 4. Subject is not able to adhere to the main protocol requirements (major protocol violations). Major protocol violations might include, but are not limited to, repeated missed infusions (more than 1 consecutive missed every 4 weeks infusion or more than 4 missed infusions per treatment period).
- The occurrence of an AE, which in the Investigator's opinion, requires the subject withdrawal from the clinical trial.
- 6. The occurrence of a confirmed thromboembolic event.
- 7. The occurrence of a confirmed clinically significant hemolysis event.
- 8. Undercurrent illness that could interfere in the study conduct or subject's safety might be threatened, at the Investigator's judgment.
- 9. Any event which in the Investigator's opinion impedes subject's participation in the study.
- 10. The subject is lost to follow-up (no attendance the scheduled study visits after randomization).

11. Subject's death.

If study participation is terminated due to an AE, the subject will be followed-up until the AE is resolved, or has been stabilized and no further change is expected, and the Investigator deems that further observations/examinations are no longer medically necessary.

If an individual is withdrawn from study due to pregnancy, the Medical Monitor must be informed by the site or by the Investigator. The pregnancy must be reported according to described procedures in Sections 9.3.8 and 9.4. If the subject had a spontaneous abortion then the event will be captured as a SAE.

Subjects who are discontinued early after randomization from the study will not be replaced.

Sites affected by the COVID-19 pandemic can refer to ANNEX 18 for extraordinary contingency measures to be implemented.

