7.1.1 Missed infusions processing

It is not allowed to prolong the treatment period. Infusions will not be postponed beyond their window period (\pm 1-week window period will be allowed for any infusion after Infusion 1).

A missed infusion will occur when a subject will not be administered with any dose of the investigational product at the scheduled infusion visit. If subject receives the investigational product at Day 1 but does NOT receive at Day 2, this will NOT be considered a missed visit.

Missed infusions will not be replaced.

During the treatment period, study subjects will be allowed to miss up to 1 consecutive infusion. More than 1 consecutive missed infusion is defined as a major protocol violation and requires subject withdrawal (Section 6.3).

A maximum of 4 missed infusions will be allowed during the treatment period (52 weeks). More than 4 missed infusions during the treatment period are defined as a major protocol violation and require subject withdrawal (Section 6.3).

Sites affected by the COVID-19 pandemic can refer to ANNEX 18 for extraordinary contingency measures to be implemented.

7.2 Medication(s)/treatment(s) permitted (including rescue medication) and not permitted before and/or during the trial

Study individuals will receive their routine therapy to treat their symptoms of PPS provided that the dose remains stable, or modified according to the standard of care and previously approved by the Investigator.

Subjects will not be allowed to receive any of the following study-specific prohibited medications: other investigational drug and human normal immunoglobulin therapy out of this clinical trial. In addition, subjects will not be allowed to receive any of the following study-specific prohibited medications unless considered medically necessary for the subject's welfare which might be given at the discretion of the investigator: narcotics or corticosteroids (except for inhaled corticosteroids taken for asthma, which will be allowed on-demand).

In any case, administration of all concomitant medication must be recorded in the appropriate section of the subject's eCRF.

No drug-drug interactions have been reported with the use of IVIG therapy.

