10.1.2 Statistical analysis of efficacy

Efficacy analysis will be primarily based on the intent-to-treat (ITT) population (see Section 10.6.1). In addition, for sensitivity analyses, efficacy analyses will also be run on the per protocol (PP) population (see Section 10.6.1).

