5.1 Data Handling

Unless otherwise noted, if an observation is missing at a specific scheduled visit/timepoint, the value at that visit will not be imputed and will be set to missing in summary tables.

Baseline will be defined as the measurement taken at the Enrollment Visit (EV)/Infusion Visit 1 (IV1) or the last measurement taken prior to the start of the study treatment if the parameter is not measured at the Enrollment Visit (EV)/Infusion Visit 1 (IV1) or there are multiple observations for the parameter at the Enrollment Visit (EV)/Infusion Visit 1 (IV1).

For table summaries, the data will be presented at the scheduled visits according to protocol. For early terminated subjects, the termination visit occurred at End of Study will be remapped to the subject's next scheduled visit for analysis and summary. Any data collected at the unscheduled visits will be listed in data listings.

5.1.1 **VAS Correction**

For cases where VAS was recorded on the scale sizes of X(mm) other than 100mm, the VAS score will be recalculated as

$$VAS_{=}VAS_{recorded} * \frac{100}{X}$$

The tracker file "IG1104 VAS scale issue 100 mm.xlsx" includes all the protocol deviations of VAS records with scales other than 100mm. The adjusted VAS score will be implemented for the cases included in the tracker file. The unadjusted and adjusted VAS scores will be presented in the relevant CSR listing with a flag to indicate which VAS scores were adjusted. A footnote will be included to explain the rescaling of the VAS scores.

5.2 **Analysis Populations**

In this study, three analysis populations are defined as:

Intent to treat (ITT) population

The Intent-to-treat (ITT) population consists of all subjects randomized.

Per-protocol (PP) population

The Per-protocol (PP) population consists of all subjects in the ITT population who have received at least 8 infusions, without having 2 consecutive missed infusions of any investigational product (test or placebo) during the treatment period, have baseline and at least one post-baseline measures of the 2MWD, and have no critical or major protocol deviations that might have impact on the primary efficacy assessment (as determined at a data review meeting prior to database lock and unblinding).

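### Breaching the missed-infusion limits ends study participation with no assessment at Week 52, and Protocol 7.1.1 and 6.3 disagree on whether that withdrawal is compulsory

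*Protocol*

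**What the plan says.** Protocol 7.1.1 tolerates isolated misses: "A maximum of 4 missed infusions will be allowed during the treatment period (52 weeks". Receiving the Day 1 infusion but not Day 2 does not count as a miss. Beyond that, the section sets two limits with the same consequence:

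- "More than 1 consecutive missed infusion is defined as a major protocol violation and requires subject withdrawal (Section 6.3"
- "More than 4 missed infusions during the treatment period are defined as a major protocol violation and require subject withdrawal (Section 6.3"

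Section 6.3, to which both point, is weaker: "A subject's participation in the study may be terminated early under the following circumstances". It gives the same two thresholds only as examples of what a major violation might be. What it ends is study participation, not just treatment.

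After withdrawal there is one visit. Protocol 4.2 says of a prematurely withdrawn subject that "he or she will be asked to attend the study centre as soon as possible thereafter". The Final/Early Discontinuation Visit in Section 5.3 includes "Physical performance: 2MWD with assessment of perceived exertion/fatigue by Borg scale immediately before and immediately after 2MWD". SAP 5.1 adds: "For early terminated subjects, the termination visit occurred at End of Study will be remapped to the subject's next scheduled visit".

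On the analysis, Protocol 10.1.2 states: "Efficacy analysis will be primarily based on the intent-to-treat (ITT) population". That set is every randomised subject (Protocol 10.6.1, SAP 5.2). The primary contrast is at Week 52, from a mixed model for repeated measures (MMRM) fitted separately in each stage (SAP 10.1). A sensitivity ANCOVA on both stages combined fills a missing Week 52 value by last observation carried forward (LOCF; SAP 10.2).

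**The concern.** An ITT analysis is meant to compare all randomised subjects whether or not they kept to treatment. Here the plan itself stops collecting the primary outcome once adherence falls below a limit. Neither document provides for stopping infusions while continuing scheduled visits.

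The MMRM then covers Week 52 by assuming that these subjects would have gone on like otherwise similar subjects who were still observed. LOCF instead carries forward a value taken around the time treatment ended. Neither has data on what happens after stopping. The per-protocol repeat excludes these subjects, and the pooled MMRM shares the primary model's assumption, so no planned sensitivity analysis tests it. If benefit fades once infusions stop, the estimate lies above the effect in all randomised subjects.

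Separately, two sites could follow 7.1.1 and 6.3 respectively and treat the same case differently.

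**Working it through.** **1. The plan's own figure.** Inputs from Protocol 10.2: 33 evaluable per arm per stage, 20% dropout, 6 m difference, SD 11 m. 33 / (1 − 0.20) = 41.25, rounded up to 42 per arm; 3 × 42 = 126 and 2 × 42 = 84. The stated sizes reproduce. Target power is not stated. A simple two-sample comparison with 66 per arm over both stages has power 0.880 at two-sided 0.05.

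**2. Where the early visit lands.** Infusions fall at Weeks 0, 4, …, 48 (13 visits), which gives 12 consecutive pairs. On-treatment 2MWDs after baseline are at Weeks 12, 24, 36 and 52 (Protocol Table 6).

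| Week of second miss | Next visit of any kind | Next visit with a 2MWD |
|---|---|---|
| 4, 8 | 8, 12 | 12 |
| 12, 16, 20 | 16, 20, 24 | 24 |
| 24, 28, 32 | 28, 32, 36 | 36 |
| 36, 40, 44, 48 | 40, 44, 48, 52 | 52 |

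- If the SAP means the next visit of any kind, the early value reaches Week 52 in 1 of 12 pairs.
- If it means the next visit with a 2MWD, it does so in 4 of 12, measured up to 52 − 36 = 16 weeks early.
- In the other 11 or 8 pairs, Week 52 is missing from the primary model. A true Week 52 measurement is obtained in none.

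These are counts of positions, not probabilities. For the total-miss limit, a fifth miss with no two in a row cannot occur before the ninth infusion visit (visits 1, 3, 5, 7, 9), that is, Week 32.

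**3. Possible overstatement.** Let f be the fraction of randomised subjects withdrawn under the rule and k the fraction of the 6 m effect kept at Week 52 after stopping. Suppose the model returns 6 m for everyone. The effect in all randomised subjects is 6(1 − f) + 6kf, so the overstatement is 6f(1 − k). Neither f nor k is in the documents. I take f from 5% to 20% and k from 0 to 1.

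| f | k = 1 | k = 0 |
|---|---|---|
| 5% | 0 m | 0.3 m |
| 10% | 0 m | 0.6 m |
| 20% | 0 m | 1.2 m |

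**4. Power if these subjects are kept.** Power = Φ(δ / (11√(2/n)) − 1.96), a simple two-sided 0.05 comparison rather than the planned combination test. With 84 randomised per arm over both stages and 20% lost, n = 67.2 and power = Φ(3.16 − 1.96) = 0.885. Keeping a fraction f off treatment gives n = 84(0.8 + f). If those kept show no effect, the mean difference becomes 6 × 0.8 / (0.8 + f).

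| f kept | n per arm | Power, full effect | Diluted difference | Power, no effect |
|---|---|---|---|---|
| 5% | 71.4 | 0.903 | 5.65 m | 0.866 |
| 10% | 75.6 | 0.918 | 5.33 m | 0.846 |
| 15% | 79.8 | 0.931 | 5.05 m | 0.827 |
| 20% | 84.0 | 0.942 | 4.80 m | 0.807 |

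Against 0.885 the change runs from −0.078 to +0.057.

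**The case against.** Several stronger readings are tempting, and the documents do not support them.

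- A reader might infer that anyone who misses infusions must leave. Up to 4 non-consecutive misses are allowed, and compulsion rests on 7.1.1 alone.
- A reader might infer that the walk data of these subjects are simply lost. The values collected before withdrawal stay in the MMRM, the early visit adds one more, and reasons for discontinuation are recorded (Protocol 5.4) and summarised (SAP 6).
- A reader might take 1.2 m as the expected overstatement. That charges the whole 20% planning dropout to this rule. The allowance has no breakdown, and Section 6.3 also covers consent withdrawal, loss to follow-up and death, which the fix cannot recover. It also assumes all benefit is lost, although the protocol sets out to measure a sustained effect 12 and 24 weeks after treatment (Protocol 8.2.1).
- A reader might infer that loss differs by arm. Protocol 4.3.2 anticipates side effects of the active product, so this is plausible. But the rule, premedication and infused volume are the same in all arms, and no dropout by arm is given. In the placebo-controlled trial of 142 patients described in Section 2.7, serious adverse events numbered 2 on placebo and 1 on IVIG.
- A reader might expect retention to bring only a gain in precision. If subjects off treatment show no effect, power falls.

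Three further objections stand. Section 6.3 also ends participation for confirmed thromboembolic and haemolytic events, and walk tests carry risks (Protocol 2.3), so continued testing needs a safety exception. ANNEX 18, cited in both sections for sites affected by COVID-19, is not in the text available and may alter the rule there. The sponsor has ended the trial early (SAP 2), so an amendment may come too late.

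None of this supplies a Week 52 measurement for the withdrawn subjects.

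**Conclusion.** The point holds as one of validity. Following the plan as written creates missing primary outcomes in subjects counted as ITT, and the analysis covers them only by assumption. The remapped early value reaches the Week 52 slot in a minority of cases and is not a Week 52 measurement. The conflict between 'requires' in 7.1.1 and 'may' in 6.3 is plain on the text and needs resolving in any case.

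The size of any bias cannot be established from the documents. The range of 0 to 1.2 m against the assumed 6 m depends on both the affected share (5–20%) and the effect kept after stopping, and both are assumptions. Retention would move power by about −8 to +6 points, so power is not the argument for it. The 20% allowance protects the sample size up to that level of loss; it does not protect against informative withdrawal.

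**What to change.** - **Protocol 6.3 and 7.1.1:** reconcile the two sections, and separate stopping investigational product from leaving the study. A subject who stops product without withdrawing consent is asked to attend the 2MWD and secondary assessments already scheduled through Week 52, unless the investigator considers an assessment unsafe. When infusions stop is not changed.
- **SAP 10:** use the values collected after stopping in the ITT analysis.
- **SAP 5.1:** state whether the next scheduled visit means the next visit of any kind or the next one with a 2MWD.
- **Where an amendment comes too late because of the early termination:** report in the SAP outputs the number of withdrawals under the missed-infusion rule by arm, and state the limitation.

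The cost is amendment and SAP wording. No new procedure is added. The downsides are some visits by subjects no longer on treatment and a possibly smaller estimated effect.

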7.2.1 Orthotic device and physical therapy

Usual care for PPS patients may also include usage of assistive and orthotic devices, and physical therapy.

Neither investigational or new assistive or orthotic device nor new physical therapy will be allowed during the clinical trial. A new orthotic device is defined as a newly prescribed intervention only. Trial subjects should perform the walking distance tests at similar

conditions throughout the clinical study, but variations from visit to visit in the use of different orthotic devices for the 2MWD and the 6MWD assessments which are not newly prescribed but rather reflect subject choice to use one of many different options the subject had previously used since before study start will not be considered a protocol deviation.

7.3 Procedures for monitoring subject compliance

Since all investigational product administrations will be performed only by study staff, compliance with the clinical trial treatment will be assessed by means of the infusions registration. Dosing information, including infusion volumes will be recorded in the *eCRF* by the study staff, which will be available for clinical trial monitors to check clinical trial compliance.

The sponsor will also instruct the study staff to document the full battery of orthotic devices the subject uses, at the point of study entry.

8 ASSESSMENT OF EFFICACY

8.1 Specification of clinical trial efficacy parameters

Primary efficacy endpoint will be:

 Physical performance (2MWD) from baseline to the end of the treatment period (at EoTV – Week 52).

Secondary efficacy endpoints will be:

- Pain (VAS of pain) from baseline to the end of the treatment period.
- HRQoL (SF-36 PCS) from baseline to the end of the treatment period.
- Endurance (6MWD) from baseline to the end of the treatment period.

Exploratory endpoints will be:

- Muscle strength of 2 newly weakened muscle groups (MMT using the MRC scale) from baseline to the end of the treatment period.
- Muscle strength of 2 newly weakened muscle groups (QMT using a dynamometer) from baseline to the end of the treatment period.
- Walking activity in daily life (pedometer) from baseline to the end of the treatment period.
- Subject's self-perceived exertion/fatigue level using the Borg scale before and after the 2MWD and the 6MWD from baseline to the end of the treatment period.
- Fatigue (FSS) from baseline to the end of the treatment period.
- HRQoL (SF-36 MCS) from baseline to the end of the treatment period.
- Blood inflammatory cytokines from baseline to the end of the treatment period.
- Sustained effect of Flebogamma[®] 5% DIF compared to placebo as measured by:
 - Physical performance (2MWD) from baseline to FU3 (Week 64) and to the FV (Week 76).
 - Pain (VAS of pain) from baseline to FU3 and to the FV.
 - HRQoL (SF-36 PCS) from baseline to FU3 and to the FV.
 - Endurance (6MWD) from baseline to FU3 and to the FV.
 - Muscle strength (MMT using the MRC scale) from baseline to the FV.
 - Muscle strength (QMT using a dynamometer) from baseline to the FV.

- Walking activity in daily life (pedometer) from baseline to the FV.
- Subject's self-perceived exertion/fatigue level using the Borg scale before and after the 2MWD and 6MWD from baseline to FU3 and to the FV.
- Fatigue (FSS) from baseline to the FV.
- HRQoL (SF-36 MCS) from baseline to FU3 and to the FV.
- Blood inflammatory cytokines from baseline to the FV.

8.2 Methods and timing for assessing, recording, and analyzing clinical trial efficacy parameters

8.2.1 Physical performance

Primary efficacy endpoint:

The treatment effect of Flebogamma[®] 5% DIF compared to placebo on physical performance will be calculated as the least squares means difference between treatment groups in the change in 2MWD from baseline (at EV/IV1) to the end of the treatment period (at the EoTV – Week 52).

Exploratory endpoint:

The sustained effect of Flebogamma[®] 5% DIF compared to placebo on physical performance will be calculated as the least squares means difference between treatment groups in the change in 2MWD from baseline (at EV/IV1) to 12 and 24 weeks after the last investigational product infusion, that is, at FU3 and at the FV.

8.2.2 Pain

Secondary efficacy endpoint:

The treatment effect of Flebogamma[®] 5% DIF compared to placebo on pain will be calculated as the least squares means difference between treatment groups in the change in VAS for pain score from baseline (at EV/IV1) to the end of the treatment period (at the EoTV – Week 52).

Exploratory endpoint:

The sustained effect of Flebogamma[®] 5% DIF compared to placebo on pain will be calculated as the least squares means difference between treatment groups in the change in VAS for pain from baseline (at EV/IV1) to 12 and 24 weeks after the last investigational product infusion, that is, at FU3 and at the FV.

